5.6 Packaging

- Etanercept will be shipped by Amgen, Inc in bulk.
- Each package of etanercept will be supplied with its diluent, Sterile Bacteriostatic Water for Injection, USP (0.9% benzyl alcohol).

5.7 Receiving, Storage, Dispensing and Return

5.7.1 Receipt of Drug Supplies

Amgen, Inc will ship the study drug to the participating Hospital's Investigational Pharmacy. Upon receipt of the study treatment supplies, an inventory must be performed and a drug receipt log filled out and signed by the person accepting the shipment. It is important that the designated study staff counts and verifies that the shipment contains all the items noted in the shipment inventory. Any damaged or unusable study drug in a given shipment (active drug or comparator) will be documented in the study files. The investigator must notify Amgen, Inc of any damaged or unusable study treatments that were supplied to the investigator's site.

5.7.2 Storage

Etanercept is not to be used beyond the expiration date stamped on the carton, dose tray label, or diluent syringe label. The dose tray containing etanercept in powder form must be refrigerated at 2°C to 8°C (36°F to 46°F), and NOT FROZEN.

Solutions of etanercept reconstituted with Amgen-supplied Bacteriostatic Water for Injection, USP (0.9% benzyl alcohol) may be stored for up to 14 days if refrigerated at 2°C to 8°C (36°F to 46°F). Reconstituted product should be discarded after 14 days as stability and sterility cannot be assured after 14 days.

5.7.3 Dispensing of Study Drug

Regular study drug reconciliation will be performed to document drug assigned, drug consumed, and drug remaining. This reconciliation will be logged on the drug reconciliation form, and signed and dated by the study team.

5.7.4 Return or Destruction of Study Drug

Study drug that remains at the end of the study will be shipped back to Amgen, Inc or destroyed on site.

At the completion of the study, there will be a final reconciliation of drug shipped, drug consumed, and drug remaining. This reconciliation will be logged on the drug reconciliation form, signed and dated. Any discrepancies noted will be investigated, resolved, and documented prior to return or destruction of unused study drug. Drug destroyed on site will be documented in the study files.

6 Study Procedures

Etanercept 0.8mg/kg (maximum 50 mg) or placebo will be given within 48 hours of initiating IVIG infusion. Randomization will be performed by internal Pharmacy, unblinded (see Pharmacy procedures). Placebo format

CONFIDENTIAL

This material is the property of the Seattle Children's Research Institute. Do not disclose or use except as authorized in writing by the study sponsor-investigator.

will be: Etanercept placebo (Amgen), TMS Lyo, B20 UnLBL 2mL vial Pink Cap. Study schema and procedures are outlined below.

TIME	0*	12-84 hours #	7 ± 3 days	14 ± 3 days	44 ± 4 days
Physical Exam	x		x	x	X
Etanercept/Placebo	x		x	x	
PK	x	x	x	X	
Cytokines	x	x	x		
CBC^	x		x	x	X
CRP	x		x	x	X
ESR	x				
Echo	x			x	X
EKG	x			x	X
AST, ALT	x		x	x	
Albumin	x		x	x	X

* Time 0 or baseline is defined as time first dose of study drug is given. Time 0 or baseline labs are almost always done before the patient has consented to the study. These labs are optional unless the patient is qualifying into the study through supplementary lab data. In general, admission laboratory values used to confirm diagnosis of KD can be used for the study, provided that they were within 24 hours prior to initiating IVIG. If a time zero lab value is not drawn as part of the clinical course prior to the patient enrolling in the study, it will not be collected and will be recorded as missing data. After enrollment, coordinators should try to retrieve extra serum obtained along with admission laboratory studies. This serum can be used for baseline pharmacokinetic assay, PK.

An EKG is normally done at time zero as part of clinical care. This EKG is optional, if an EKG is not performed at baseline it will not be recorded as a protocol deviation.

Parents are to record temperature after discharge daily between 4PM and 6PM for two weeks, as well as if and when they believe child has fever, and notify study coordinator if $> 38.0^{\circ}\text{C}$. If patient temperature $> 38^{\circ}\text{C}$ and the investigator or treating cardiologist feels the patient needs to be readmitted, an extra study visit will occur within 12-24 hours of re-admission with PE, CBC, CRP, ESR, Echo, and ECG. This extra visit concurs with clinical guidelines for standard of care. ^CBC includes WBC with differential and platelet count. Parents are also to notify coordinator if any sign of infection. # PK, for this time point will be 48 hours (window 12 – 48 hours) after Etanercept.

We will define failure to respond to IVIG using the AHA guidelines: as persistent fever $> 38.0^{\circ}\text{C}$ extending beyond 36 hours after completion of IVIG infusion or recurrent fever $> 38.0^{\circ}\text{C}$ after 36 hours of completion of the initial IVIG infusion.

All patients with disease-related complications will receive standard care by their primary Pediatric Cardiologist and other treating physicians. This will include anticoagulation therapy when the primary Cardiologist feels it is necessary. AHA/AAP guidelines recognize the use of various types of anti-coagulation. Low dose ASA as described above represents the primary antiplatelet therapy. "Clopidogrel in combination with aspirin has been shown to be more effective than either agent alone in preventing vascular events in both coronary and cerebral territories in adults (the Clopidogrel in Unstable Angina to Prevent Recurrent Events study)." However, there is no evidence in children that this is effective therapy. Many Pediatric Cardiologists use heparin infusion often

CONFIDENTIAL

This material is the property of the Seattle Children's Research Institute. Do not disclose or use except as authorized in writing by the study sponsor-investigator.

followed by Warfarin for rapidly expanding or giant coronary artery aneurysms. The current protocol does not preclude their use. We have proposed an adjunctive therapy for KD. Accordingly, we are not interfering with standard of care, and do not specify concomitant medications. All medications prescribed by primary care providers are permitted. Additionally, no live vaccine may be given for at least 11 months after receiving IVIG as recommended by the American Academy of Pediatrics.

Treatment with high dose steroids and/or infliximab during the course of the study is permitted if recommended by Rheumatology for the treatment of recurrent Kawasaki Disease.

6.1 Visit 1 - Hospital

The patient is admitted into the hospital. Patient family is referred to the research staff for study discussion and consent. The patient is screened for eligibility, study discussion is conducted, and consent is obtained. Assent will also be obtained if deemed required by IRB. (see section entitled "Protection of Human Subjects").

All patients will receive standard treatment for KD as stated in the AHA-AAP guidelines. This includes IVIG 2 gm/kg over 10 hours or longer if interruptions occur in the infusion and high dose ASA, administered at 80 to 100 mg/kg per day in 4 doses until patients have been afebrile for 48 hours. Subsequently, patients will continue low dose ASA 3-5 mg/kg per day until 6 weeks or longer at the discretion of the treating Pediatric Cardiologist.

The blood for the baseline measurements can be drawn with the IV start or from the IV line. Labs obtained upon hospital admission will be used for baseline data. The PK blood sample will be processed and stored for later shipping by the lab or study personnel, while the other blood samples shown in study schema are sent to the central hospital laboratory for processing and results. An Echo and EKG are performed. A nurse administers a subcutaneous injection of study drug or equivalent volume of placebo at the appropriate dosage 0.8 mg/kg (maximum 50 mg). Etanercept must be administered within 48 hours after initiating IVIG therapy, and as early as possible. Etanercept should not be given prior to starting IVIG infusion. After discharge, the parents of the patient are to record daily temperatures between 4PM and 6PM for the next two weeks in a log provided by the nurse coordinator. Thermometer will be given to family if not already available or provided by hospital and coordinator will instruct patients regarding the proper procedure for taking and recording temperature. If the parents believe that their child has a fever, they are to record the child's temperature regardless of the time of day and notify the study coordinator if temperature is $> 38.0^{\circ}\text{C}$. If the study coordinator is unavailable the family should call the on-call cardiologist. If the child is readmitted, an extra study visit will occur within 12-24 hours of the patient being readmitted, and a physical exam, CBC, CRP, ESR, ECG, and Echo will be completed. Parents are to notify the study coordinator if they find any signs of infection in the patient.

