1.4 Dose Rationale

Etanercept is slowly absorbed after subcutaneous (SC) injection, and the absolute bioavailability is approximately 58% in adults³⁷. Etanercept has a relatively small volume of distribution of 12 ± 6 and is slowly absorbed to reach its peak serum concentration about 50 hours after injection and cleared from the body with a reported median half-life of 115 hours³⁷. The recommended dosing regimen for JRA patients (4-17 years) at the time of its initial approval was 0.4 mg/kg (up to 25 mg) twice weekly by SC injection⁴⁰.

Figure 2 A. Data below is extracted from Yim et al, and shows overlay of observed and simulated data for children in JRA group receiving 0.4 mg/kg twice weekly.

[figure not shown]
[figure not shown]

Figure 2B. Data from 5 patients in pilot study receiving 0.4 mg/kg etanercept starting immediately after IVIG infusion and then weekly x 2. 1000 ng/ml = 1 mg/L

However, based on its slow absorption and elimination and pharmacokinetic (PK) profile, a doubled dose with a half-frequency regimen (ie, 0.8 mg/kg [up to 50mg]) of a once-weekly SC injection was sought and FDA approved for patient convenience. PK simulation studies using data from juvenile rheumatoid arthritis (JRA) patients receiving 0.4 mg/kg SC twice weekly show similar steady-state levels at 1 and 8 weeks for children receiving 0.8 mg/kg⁴¹. After repeated subcutaneous treatment mean serum etanercept concentration was 2100 ng/ml (range 700 to 4300 ng/ml). Although eighteen JRA patients were between age 4 and 8 years, relatively few patients were under age 5 years. The data in Figures 2 A and 3A illustrate drug concentrations from the JRA population and are extracted from Yim et al⁴¹. These can be compared to the PK profiles for the two different drug doses used in the pilot study (data shown in Figs 2B and 3B). The pharmacokinetic profiles for 5 pilot study patients, receiving 0.4mg/kg weekly (Figure 2.B), show lower than therapeutic levels, defined by 5th to 95th %tile range in shown in 2A for JRA patients receiving twice weekly doses. Steady state concentrations after 0.8 mg/kg after 1 week (Figure 3 B) are within the simulated and therapeutic range calculated for the JRA group (3A).

[figure not shown]

Figure 3A. The data extracted from Yim et al represents simulation for 0.8 mg/kg (once weekly) and 0.4 mg/kg (twice weekly). These simulations consider drug levels after 8 weeks of therapy,

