3.1 Primary clinical endpoint

The primary aim of this study is to determine if Etanercept (Enbrel) 0.8 mg/kg given subcutaneously to patients with acute Kawasaki Disease will reduce the incidence of IVIG refractoriness as defined in the joint American Heart Association and American Academy of Pediatrics Endorsed Clinical Report: “Refractory Kawasaki Disease will be defined as the persistence or recrudescence of fever ($\geq 38.0^{\circ}\text{C}$ or 100.4°F) at least 36 hours after the end of the IVIG infusion”³.

Rationale for primary endpoint: Refractory KD is an objective clinically important and easily measured parameter. Orphan product indications by the FDA are likely to be influenced by clinical parameters as opposed to sonographic measures. Refractoriness increases risk of coronary artery disease, number of hospitalization days and cost of treatment¹¹. Several studies have unsuccessfully used coronary artery dilation (CAD) as a primary endpoint to evaluate adjunctive therapy^{13, 14}. Risks in using CAD are: intra-observer and inter-observer variability. Although, we will have a central echocardiographic reader, subjectivity is introduced by the sonographer actually performing the study. Coronary artery dimensions can be skewed by angle, machine settings and other parameters beyond the control of the reader. Therefore, coronary artery dilation parameters will be relegated to secondary endpoints.

CONFIDENTIAL

This material is the property of the Seattle Children's Research Institute. Do not disclose or use except as authorized in writing by the study sponsor-investigator.

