* PPD testing will not be performed in these patients. Reactivation of chronic granulomatous disease including tuberculosis from chronic treatment with TNF α antagonists is a valid safety concern.³¹ The risk of TB reactivation for patients on etanercept therapy still requires clarification. A recent review at Cook County and Rush Hospital in Chicago showed that none of the 48 patients with positive PPDs who were treated with etanercept for average of 17 months developed active TB⁵³. Additionally, Mohan et al reported the earliest reactivation occurred after 1 month of initiating etanercept with a mean of 11.5 months⁵⁴. Use of additional immunosuppressive agents other than etanercept was a risk factor. Our cohort will receive a very short course (~ 2 weeks) of etanercept and will not receive other immunosuppressive drugs, thereby markedly reducing the already very low risk of TB in this population. For instance, the incidence of TB in King County, WA in children is 1 -2.5/100,000 or 8-12 per year. To be effective in acute Kawasaki Disease, etanercept must be given at the same time or immediately after IVIG treatment. We cannot delay while awaiting mandatory 48-72 hours for results of skin testing. The new Quantiferon gold test for TB is not yet widely available (and not in Seattle) and would still require at least 24 hours. We have considered placing TB skin testing after initial dose and discontinuing if positive. However, it is likely that TNF- α antagonism could affect the test and provide a false negative. Therefore patient exclusion will be performed based on high risk history, such as immediate family or household member with positive PPD.

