The pharmacist and pharmacy technical staff will be not be blinded. The study statistician will provide each site pharmacy with randomization table. Pharmacists will supply each patient with drug or placebo, both provided by Amgen in separate labeled vials. Pharmacists will draw dose in syringes and dispense to nursing for administration. Drug accountability will be monitored by the CRO as described below. Study randomization codes and links to patients will be kept in secure records in pharmacy. All other study personnel involved in administration of drug will be blinded.

6.9 **IVIG Retreatment**

As noted in section 3.1: The primary aim of this study is to determine if Etanercept (Enbrel) 0.8 mg/kg given subcutaneously to patients with acute Kawasaki Disease will reduce the incidence of IVIG refractoriness as defined in the joint American Heart Association and American Academy of Pediatrics Endorsed Clinical Report: "Refractory Kawasaki Disease will be defined as the persistence or recrudescence of fever ($\geq 38.0^{\circ}\text{C}$ or 100.4°F) at least 36 hours after the end of the IVIG infusion"³. Persistent or recrudescent fever is the sole criteria for determining the need for retreatment. The clinical decision can be supported by persistent symptoms and persistent elevation or rebound of inflammatory parameters such as CRP. The protocol requires waiting at least 36 hours after completing the first IVIG dose before initiating the second dose.

7 Statistical Design and Analysis

The primary outcome variable is the Y/N determination of whether the subject is refractory to IVIG treatment, defined as persistence of fever $>38^{\circ}\text{C}$ beyond 36 hours from completion of IVIG treatment, or recurrence of fever within 10 days, and clinical decision to retreat with IVIG. Chi-square testing will be used to compare the proportions of subjects classified as refractory to IVIG treatment between the group randomized to receive Etanercept as an adjunctive therapy and the group randomized to receive placebo. If necessary (due to low cell counts), a Fisher's Exact test can be substituted. Stratified versions of the chi-square and Fisher's tests are available in StatXact (Cytel Incorporated) to allow stratification by center.

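### The 48-hour limit on the first dose lets a patient be randomized and first dosed after the primary endpoint can already have been met; a small eligibility rule and one supportive analysis would close the gap

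*Combined protocol and SAP*

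**What the plan says.** - **First dose.** Section 6.1 states: "Etanercept must be administered within 48 hours after initiating IVIG therapy, and as early as possible". It also rules out dosing before the infusion starts. Sections 3.3 and 6 repeat the 48 hours, counted from the start of IVIG. This is the only numerical limit on the first dose.
- **Infusion.** Section 6.1 describes standard treatment: "This includes IVIG 2 gm/kg over 10 hours or longer if interruptions occur in the infusion". Section 1.1 notes that infusions are interrupted for fever spikes.
- **Endpoint.** Section 3.1 defines refractory disease by persistent or returning fever "at least 36 hours after the end of the IVIG infusion". Section 7 uses the same 36 hours, adds recurrence within 10 days, and also requires a clinical decision to retreat.
- **Retreatment.** Section 6.9: "The protocol requires waiting at least 36 hours after completing the first IVIG dose before initiating the second dose". Under section 6.6 (treatment for refractoriness), study drug continues after retreatment.
- **Timing and effect.** The note on tuberculosis testing at the end of section 4.2 says: "To be effective in acute Kawasaki Disease, etanercept must be given at the same time or immediately after IVIG treatment". Section 1.4 describes etanercept as "slowly absorbed to reach its peak serum concentration about 50 hours after injection".
- **What is absent.** Nothing in sections 4.2, 4.4, 6.1 or 7 says what to do with a patient who meets the fever criterion, or for whom retreatment is decided, before the first dose. Section 7 plans no analysis by time of first dose.

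**The concern.** The dosing limit runs from the start of IVIG and the endpoint clock runs from its end. The two are never reconciled, and for a short infusion they cross: a patient can be eligible, randomized and dosed on time when the event that the drug is meant to prevent has already happened.

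Such a patient is a failure in either arm, whatever the drug does. A patient dosed a few hours earlier is in a similar position, because little drug has been absorbed when failures begin to count. Dosing is blinded, so there is no reason for late doses to be commoner in one arm. What is at stake is therefore sensitivity: failures that treatment cannot reach move the two refractory rates closer together and cost power.

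**Working it through.** All times are hours from the start of IVIG.

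**Inputs.** Infusion length D, at least 10 h (6.1). Endpoint offset 36 h after the infusion ends (3.1, 7). Earliest retreatment 36 h after the infusion ends (6.9). Latest first dose, hour 48 (3.3, 6, 6.1). Peak concentration about 50 h after injection (1.4).

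**Step 1: when failures can first count.** Opening hour = D + 36. Overlap with the dosing window = 48 − (D + 36) = 12 − D, where positive.

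| D | Endpoint opens | Overlap | Exposure at opening if dosed at hour 48 |
|---|---|---|---|
| 10 h | hour 46 | 2 h | none (dose is 2 h too late) |
| 12 h | hour 48 | 0 | 0 h |
| 14 h | hour 50 | none | 2 h |
| 16 h | hour 52 | none | 4 h |
| 24 h | hour 60 | none | 12 h |

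Since D is at least 10 h, the overlap never exceeds 2 h. Under section 3.1 the fever alone makes the patient refractory. Section 7 also needs a decision to retreat, and retreatment is allowed from the same hour.

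**Step 2: exposure before the endpoint opens, 10-hour infusion.** Exposure = 46 − dose hour.

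| First dose | Exposure at hour 46 | Approximate peak (dose hour + 50) |
|---|---|---|
| hour 0 | 46 h | hour 50 |
| hour 10 | 36 h | hour 60 |
| hour 24 | 22 h | hour 74 |
| hour 36 | 10 h | hour 86 |
| hour 48 | none | hour 98 |

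Hour 48 is 48 − 10 = 38 h after the infusion ends, which is hard to describe as immediately after IVIG.

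**Step 3: what dilution could cost (illustration only).** The documents give no share of patients dosed late and no split of failures into persistent and recurrent fever, so both are assumed. I take the planned 25% versus 8% with 97 per group (4.3) and a two-sided 5% test by the pooled two-proportion formula. The plan states 80% power for this row; the formula gives 90%, so the falls matter rather than the levels.

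Suppose a share g of patients is dosed too late to change persistent-fever failures, and a share f of failures is persistent fever. Etanercept rate = 0.08 + (0.25 − 0.08) × f × g = 0.08 + 0.17fg. For f, I take 13%/23% = 0.565 from two different cohorts in section 1.1, with a range of 0.30 to 0.80.

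| g | Etanercept rate at f = 0.565 | Power (range over f = 0.30 to 0.80) |
|---|---|---|
| 0 | 8.0% | 90% |
| 5% | 8.5% | 87% (88% to 86%) |
| 10% | 9.0% | 85% (87% to 83%) |
| 25% | 10.4% | 76% (83% to 69%) |

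A harsher assumption, that late-dosed patients lose all benefit including on recurrence (f = 1), gives 86% at g = 5% and 81% at g = 10%. For failures in the strict overlap alone, g should be close to zero.

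**The case against.** The strongest reply is that 48 hours is an outer tolerance and not the target. The same sentence in 6.1 directs early dosing, 3.3 names dosing concurrent with IVIG first, 5.2 starts treatment at diagnosis, and 4.4 has patients screened before IVIG. Nothing suggests that late doses would be common. Febrile patients are also the ones whose infusions are interrupted, which shrinks or removes the overlap. This stands, and it is why the effect is probably small. It does not close the gap: a dose at hour 47 complies.

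Four stronger readings are tempting, and the documents do not support them.

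- **A reader might infer that the section 4.2 note makes the 48-hour window a contradiction.** The note explains why tuberculosis testing is omitted; it is not a dosing rule. The skin-test sentence, "We cannot delay while awaiting mandatory 48-72 hours for results of skin testing", is compatible with a 48-hour limit. For the blood test, said to be one that "would still require at least 24 hours", the first reason given is poor availability. The note sits awkwardly with a dose 38 h after the infusion, and no more can be drawn from it.
- **A reader might infer that the window must be cut, for example to 6 hours after the infusion ends or 24 hours after IVIG starts.** Neither figure has a source in the documents. Peak concentration does not decide between rules either, since even a dose at hour 0 peaks near hour 50, after hour 46. The recruitment cost is unknown.
- **A reader might take the power table as an expected loss.** The late-dosed shares are assumed, and no hour is established at which a dose becomes ineffective.
- **A reader might infer that a null result could never be separated from late dosing.** The attachments list forms for IVIG treatment, IVIG retreatment and temperatures. Their fields are not shown, so the necessary times may already be collected.

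Late doses may also still prevent recurrent fever, which counts up to 10 days.

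**Conclusion.** The gap is real and narrow. With an infusion shorter than 12 hours, the plan allows randomization and first dosing up to 2 hours after the refractory-fever criterion can be met and retreatment allowed, and it has no rule for such a patient. Such a failure cannot be prevented by etanercept but counts in the primary endpoint. Beyond the strict overlap, doses late in the window leave little exposure before failures count: 10 h for a dose at hour 36 after a 10-hour infusion, 4 h for a dose at hour 48 after a 16-hour infusion.

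The direction is dilution toward the null, with no advantage to etanercept. The size cannot be established from the documents and is probably small. The clock arithmetic rests only on stated limits; any figure for lost power rests on assumed shares.

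**What to change.** 1. In 3.3, 6 and 6.1, keep the 48-hour window but require randomization and first dose before 36 hours after the end of the infusion, whichever limit comes first. For a 10-hour infusion this means before hour 46; from 12 hours upward the 48-hour limit governs.
2. Bar randomization of any patient who already has qualifying fever or for whom retreatment has been decided. The time limit covers the fever if it is followed; the explicit bar also catches retreatment decisions made earlier.
3. Use the clock times of IVIG start, IVIG end, first dose and first qualifying fever, and add to the case report form any that it lacks.
4. In section 7, prespecify a supportive analysis of the primary endpoint by time from IVIG start to first dose. That interval is fixed when the first dose is given, so it cannot depend on the effect of study drug.

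**Cost.** At most a few late-consenting patients become ineligible, and there is one extra analysis. No visit, sample or additional patient is needed. A tighter cap (6 hours after the infusion ends, or 24 hours after IVIG starts) is a recruitment trade-off for the sponsor to weigh and is not a required correction.
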